Primary endpoint: The primary endpoint is the Th1/Th2 ratio. Th1/Th2 ratio will be compared between the two groups. The trial will be considered a success if the Th1/Th2 ratio is statistically significantly higher in the GM-CSF treated group.

Sample Size and power: There will be 10 patients in each group. It is expected that this treatment will have a considerable effect on the Th1/Th2 ratio. If it does not, it will not be of further interest. A sample size of 10 in each group will have 80% power to detect an effect size of 1.325 using a two group t-test with a 0.050 two-sided significance level. The effect size is the expected difference in the means divided by the pooled standard deviation.

Analysis plan: The primary endpoint will be compared between the two groups using a two-sample t-test. If the distribution of the Th1/Th2 ratios is considerably skewed, the analysis will be done on the log transformed values. If the log transformed distribution is also skewed, then a rank-sum test will be used to compare the Th1/Th2 values between the two groups. Given the small sample size, all other analyses will be exploratory. Continuous measurements will be summarized with means and standard deviations and compared between groups using a two-sample t-test (on log transformed data if necessary). Categorical variables will be summarized as frequencies and relative frequencies and will be compared between groups with a Fisher's exact test. We will also summarize disease-free survival with Kaplan-Meier curves. The adverse event data will be reported as frequencies and relative frequencies. The number/proportion of patients with Grade 3+ AEs will be compared between the two groups using Fisher's exact test. All tests will be two-sided and a p-value of 0.05 will be considered statistically significant.

PROJECTED RESULTS

We will compare demographic, clinical and pathological variables between the two cohorts. Given the unselected nature of this study we anticipate that the two groups will be comparable.

We anticipate that the gene expression phenotype (as analyzed by RT-PCR) and the immune milieu (as analyzed by flow cytometry) of the SLN in patients who received preoperative GM-CSF will have maintained a more Th1 biased immune profile. We

anticipate that the improved Th1:Th2 profile will not only apply to the SLN but to neighboring lymph nodes as well.

Data Management Plan

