Appendix

GM-CSF Pharmacology

GM-CSF Preclinical Toxicology

GM-CSF Pharmacokinetics in Normal Subjects

Protocol Title	Neoadjuvant GM-CSF treatment and modulation of the immune		
	cell profile of the SLN in melanoma (as above)		
# Site and Names:	One Site: Mayo Clinic Rochester		
Study Schema:	Twenty patients with a primary melanoma 1-4mm Breslow depth		
	will be randomized to either undergo standard care (10 patients),		
	or be treated with 14 days of GM-CSF administered		
	subcutaneously daily in a dose of 125 μ g/m ² preoperatively (10		
	patients), prior to sentinel lymph node biopsy. The regional lymph		
	nodes will undergo detailed analysis defining their immune		
	features		
Trial Objective:	features To characterize and compare the regional nodal immune features		
Trial Objective:	features To characterize and compare the regional nodal immune features of the GM-CSF treated patients, including the Th1/Th2		
Trial Objective:	features To characterize and compare the regional nodal immune features of the GM-CSF treated patients, including the Th1/Th2 environment, with the regional immune environment of the		
Trial Objective:	features To characterize and compare the regional nodal immune features of the GM-CSF treated patients, including the Th1/Th2 environment, with the regional immune environment of the control cohort		
Trial Objective:	features To characterize and compare the regional nodal immune features of the GM-CSF treated patients, including the Th1/Th2 environment, with the regional immune environment of the control cohort		
Trial Objective: Study Design:	features To characterize and compare the regional nodal immune features of the GM-CSF treated patients, including the Th1/Th2 environment, with the regional immune environment of the control cohort Open-label, single-center, randomized controlled trial		
Trial Objective: Study Design: Accrual Goal:	features To characterize and compare the regional nodal immune features of the GM-CSF treated patients, including the Th1/Th2 environment, with the regional immune environment of the control cohort Open-label, single-center, randomized controlled trial 20 patients		

PROTOCOL SYNOPSIS

Followup:	30 days postoperatively			
Inclusion Criteria:	Histologically confirmed, 1-4mm Breslow depth			
	melanoma			
	Clinical stage I or II disease			
	Undergoing sentinel lymph node biopsy			
Exclusion Criteria	Clinical stage III or IV disease			
	Immunosuppressive therapy in the past 6 weeks (e.g.			

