- Autoimmune disease: Patients with a history of inflammatory bowel disease are excluded from this study as are patients with a history of immunologic disease (e.g. rheumatoid arthritis, scleroderma, systemic lupus erythematosus, autoimmune vasculitis, motor neuropathy considered of autoimmune origin)
- 3) Any underlying medical conditions which, in the opinion of the investigator, will make the administration of GM-CSF hazardous or obscure the interpretation of

adverse events; such as, psychological, familial, sociological or geographical conditions potentially hampering compliance with the study protocol and followup schedule

- 4) Any vaccination therapy within 4 weeks prior to GM-CSF administration
- 5) Concomitant therapy with any of the following within the past 3 months: GM-

CSF, interferon, other non-study immunotherapy regimes; cytotoxic

chemotherapy

- Immunosuppressive mediations within the past 6 weeks including:
 - High dose steroids (>5mg/day)
 - TNF-inhibitors
 - o Methotrexate
 - o IL-1Ra antagonist
- 6) Active or chronic infection with HIV, hepatitis B or hepatitis C
- 7) WOCBP who are unwilling or unable to use an acceptable method to avoid

pregnancy for the entire study period and 2 weeks after cessation of the study drug.

8) Prisoners or subjects who are compulsorily detained

Study Scheme

Patients will be randomized to control or intervention group. Patients will be treated with 14 days of GM-CSF self-administered subcutaneously daily for 14 days in a dose of 125 μ g/m2. Patients will be instructed in the self-administration of GM-CSF and after they have demonstrated competency with the procedure, they will self-administer the treatment at home. Patients will undergo surgery within 1 day to 5 days after cessation of the GM-CSF therapy.

Surgical intervention will follow our institutional standard of care, including wide local excision of the primary melanoma according to National Comprehensive Cancer Center (NCCN) guidelines and SLN biopsy (7).

DETAILS OF PROCEDURES

This study is divided into five phases (Recruitment, Preoperative treatment, Surgery, Laboratory analysis, Followup) with associated procedures that will be performed at specific time points as described within the following sections.

Recruitment

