As soon as a patient is considered for this study and prior to any study procedures, the patient will have the nature of the study explained to him or her, and will be asked to give written informed consent and Health Insurance Portability and Accountability (HIPAA) authorization. Informed consent must be obtained prior to any procedures that do not constitute part of the patient's normal care.

Patients will be introduced to the project at their meeting with their surgeon. (S)he will outline the project to them and answer any questions. The study coordinator will meet with the patient to discuss the trial further and formal consent obtained if the patient wishes to be part of the study. Following informed consent and after the patient decides to participate in the study, the patient will be randomized into either the intervention or control arm. The following checks will be completed by the surgeon and by the study coordinator.

- Eligibility confirmation
- Histologic diagnosis of malignant melanoma (based on original biopsy, no new biopsies required)
- Medical history
- Physical examination
- Concomitant medication review

A surgical date will be set and based on this, patients enrolled in the GM-CSF arm will be given written directive on the start and stop date of the GM-CSF.

We will prospectively record the demographic, clinical and pathological data of all patients including age, sex, primary location, lymph node basin, if the SLN and non SLN analyzed were positive or negative for metastatic disease, Breslow depth, Clark's level, mitotic rate, ulceration, presence of regression, and tumor infiltrating lymphocytes, if any residual disease is present at the primary site at the time of WLE and time period between original biopsy confirming melanoma and the sentinel lymph node procedure. The 10 second radioactive count of the SLNs and if the SLN is blue or not will be captured. If the SLN is positive the size of the metastatic focus will be recorded. All SLNs will be sent to pathology as is our standard. Only tissue from SLN#1 and if applicable SLN#2 will be submitted for research purposes. All data will be stored in a secure file on the Mayo intranet.

Preoperative treatment

Patients who have been randomized to undergo GM-CSF treatment preoperatively will be educated in administration of subcutaneous GM-CSF.

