For GM-CSF, toxicity is assessed according to the NCI CTCAE, Version 4. The major nonhematologic toxicities expected for GM-CSF are injection site reactions and a flu-like syndrome. GM-CSF must be discontinued if the patient has an allergic reaction which, in the opinion of the investigator would pose an unacceptable hazard to the patient. GM-CSF will also be discontinued for any grade 3 or greater AE or any unacceptable toxicity attributed to GM-CSF at the request of the patient.

Subjects must be discontinued from any further study therapy for the following reasons:

- Any clinically significant adverse event (grade 3 or grade 4)
- Any clinical adverse event which in the opinion of the investigator indicates that continued treatment is not in the best interest of the patient
- Intercurrent illness which would, in the judgement of the investigator require discontinuation of the drug
- Noncompliance with respect to taking the drug

Patients who have a drug related Grade 3 or greater adverse event at the time of discontinuation from study treatment will continue to be followed until resolution of the event or until the event is considered irreversible.

Subjects must be discontinued from the study therapy AND withdrawn from the study for the following reasons:

- Withdrawal of informed consent for any reason
- Patient request to withdraw from the study
- Pregnancy
- Termination of the study
- Imprisonment or the compulsory detention of the patient.

Stopping rules for the study

The trial will be stopped if 3 consecutive patients or at any time after 6 patients have been treated, if 30% of patients, have been required to be removed from the study due to drug-related toxicities, accrual will be halted and the study reviewed by the DSMB.

Prohibited therapies

Patients may not use any of the following during the study:

- Immunosuppressive agents, except if needed to treat AEs or provided during anesthesia administration
- Chronic systemic corticosteroids
- Any non-oncology vaccine therapies used for the prevention of infectious diseases
- Other investigational agents

STATISTICAL CONSIDERATIONS

Randomization: Patients will be randomized in a 1:1 fashion using a varying permuted block randomization (block sizes of 2 and 4).

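### The Recruitment section prints randomisation before the eligibility checks in an open-label, single-site trial and describes no allocation concealment; eligibility should be documented before the arm is released

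*Combined protocol and SAP*

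**What the plan says.** The Protocol Synopsis describes the trial as "Open-label, single-center, randomized controlled trial", with 20 patients at one site.

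Under Details of Procedures, Recruitment, the steps are printed in this order:

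1. Informed consent.
2. Randomisation, followed at once by the checks: "the patient will be randomized into either the intervention or control arm. The following checks will be completed by the surgeon". The coordinator shares the checks with the surgeon.
3. The list of checks, which opens with "Eligibility confirmation" and continues with histology, history, examination and medication review. No time is attached to the list.
4. The surgical date: "A surgical date will be set and based on this, patients enrolled in the GM-CSF arm will be given written directive" on when to start and stop the drug.

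The Inclusion and Exclusion Criteria suggest a different order. Meeting all inclusion criteria is a condition of participation, and an exclusion bars entry to the study.

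One exclusion is a matter of judgement. It covers conditions that, "in the opinion of the investigator, will make the administration of GM-CSF hazardous", and it extends to circumstances "potentially hampering compliance with the study protocol".

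Statistical Considerations, Randomization, specifies 1:1 allocation "using a varying permuted block randomization (block sizes of 2 and 4"). The document does not say who holds the list, how an arm is released, or whether upcoming assignments are concealed.

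**The concern.** Randomisation protects a comparison only if the decision to enter a patient is made without knowledge of the arm. The Recruitment section, read as a sequence of steps, reverses this: the arm is assigned and eligibility is confirmed afterwards.

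That matters here because one exclusion asks for an opinion about how hazardous GM-CSF would be for this patient and how well the patient would comply. Those questions may be answered differently for a patient already known to be a control than for one about to receive the drug. Any removal of patients on that basis could differ by arm, and the comparison has only 10 patients per arm.

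The surgery date raises a similar but lesser question. It is printed after randomisation, the drug course ties it to the treatment start in one arm, and no corresponding timing rule is given for controls.

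Even if the checks come first, staff at one open-label site see the earlier assignments and can guess the next arm. With small blocks of published size, they can sometimes know it.

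**Working it through.** **Order of steps.** Setting the sections side by side:

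| Step | Recruitment section | Inclusion and Exclusion Criteria |
|---|---|---|
| Eligibility | Listed after randomisation, no time given | A condition of participation and entry |
| Surgical date | Set after the checks are listed | Biopsy must be scheduled, which may mean only that it is planned |

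The eligibility row is a real tension. The date row is not a clear contradiction.

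**The plan's own power figure.** Inputs from Statistical Considerations are 10 per arm, effect size 1.325 and two-sided 0.05. For a two-sample t-test, df = 18, noncentrality = 1.325 × √(10×10/20) = 2.963 and the critical value is 2.101. Power is 80.0%, matching the stated 80%. Changing the order of steps alters none of these inputs.

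**Predictability if the checks come first.** The block sizes are stated but their mix is not. Let q be the share of blocks of size 4, assumed to lie between 25% and 75%. The guesser sees every earlier arm, names the arm with fewer patients so far, and tosses a coin when the arms are level.

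- Block of 2: 1/2 + 1 = 3/2 correct guesses.
- Block of 4: 1/2 + 2/3 + 2/3 + 1 = 17/6 correct guesses.
- First two patients of a block of 4 cut off at patient 20: 1/2 + 2/3 = 7/6.

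Let F(n) be the expected number of correct guesses in n patients:

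F(n) = (1−q)[3/2 + F(n−2)] + q[17/6 + F(n−4)], with F(0) = 0 and F(2) = (1−q)(3/2) + q(7/6).

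**Certain calls.** Someone who knows that the sizes are 2 and 4 is certain only when a block opens with two patients in the same arm. This happens in 1/3 of blocks of 4, and the third and fourth patients are then known. Each complete block of 4 therefore contributes 2 × 1/3 = 2/3 of a certain call on average:

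C(n) = (1−q)C(n−2) + q[2/3 + C(n−4)], with C(0) = C(2) = 0.

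| q | Correct of 20, F(20) | Share | Certain of 20, C(20) |
|---|---|---|---|
| 0.25 | 14.63 | 73% | 1.2 |
| 0.50 | 14.37 | 72% | 2.1 |
| 0.75 | 14.19 | 71% | 2.7 |

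A coin toss gives 10 of 20. The tally rule does not use the block sizes, so hiding them leaves the second column unchanged and removes only the last column.

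**Surgery date.** With 14 uninterrupted daily doses, the first on day 0 and the last on day 13, and surgery 1-5 days after the last dose, surgery falls on days 14-18. A date recorded before allocation may therefore have to move if the patient is assigned to GM-CSF.

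**The case against.** The strongest reply is that this is a matter of drafting. The Recruitment section does not say that the checks are done after randomisation; it only prints them there. The eligibility sections state a rule, and an explicit rule should outweigh sentence order in a narrative paragraph. This stands to the extent that the point is an ambiguity and not a stated procedure. It does not remove the need to fix the text, because site staff work from the procedures section, and the judgement-based exclusion is the kind that should not be left open.

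A second reply is that any difference in surgical timing would be visible. The Recruitment section already records the interval from original biopsy to the sentinel node procedure for every patient, and Projected Results plans to compare clinical variables between the cohorts. That is correct, but it detects an imbalance and does not prevent one.

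A third reply is that moving the block sizes gains little. The figures above agree, which is why it is a secondary fix.

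Some stronger readings are tempting, and the documents do not support them:

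- A reader might infer that the arm is known for all 20 patients when eligibility is judged. That only restates the assumption that the printed order is followed.
- A reader might cite the Timeline, which places the surgical consult before group assignment. It mentions neither the eligibility checks nor the setting of a date, so it is not evidence on either.
- A reader might count calls made with high but incomplete confidence. That requires the guesser to know the mix of block sizes, which is not stated.
- The vaccination exclusion, "Any vaccination therapy within 4 weeks prior to GM-CSF administration", is dated from an event that controls do not have. This is a separate wording gap for the investigators to reconcile; it does not show that eligibility is judged after allocation.

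**Conclusion.** The point holds as an ambiguity that should be corrected. The printed sequence permits eligibility, including an opinion-based exclusion about GM-CSF, to be judged with the arm known in an open-label single-site trial. The eligibility sections point the other way, and no concealment method is described.

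A reader might infer that the trial is biased. Nothing in the documents shows this, in size or in direction, and the stated 80% power is unchanged.

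The part that can be quantified concerns prediction of the next arm: about 14.2-14.6 correct guesses of 20, and about 1-3 certain calls. These figures assume that staff see all earlier arms and that blocks of 4 make up 25-75% of blocks; the certain calls also assume that staff know the block sizes. A reader might also infer that hiding the sizes would make allocation unpredictable. It would not, because the guess rate stays near 72%. The order of steps and the concealment method matter more.

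**What to change.** **Main change.** Reorder the Recruitment section so that all eligibility checks are completed and documented before the allocation is requested and released, and reconcile it with the Inclusion and Exclusion Criteria. State how the arm is released, and have the list held by someone who does not enrol patients.

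**Secondary changes.**

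- Record the planned surgery date before release, and document any later change with its reason. Some GM-CSF dates will still move to fit the drug course, so this makes arm-dependent timing auditable but does not remove it. The surgical schedule itself stays with the investigators.
- Move the block sizes from Statistical Considerations to a document that enrolling staff do not see. The blocks of 2 and 4 can stay.

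Separately, the investigators should reconcile how the vaccination exclusion is dated for controls.

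**Cost.** A reordered paragraph, one restricted document and a short record of date changes. No extra patients are needed, and 10 per arm and 80% power are unaffected.

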This study involves removing 1 half of one (1-2mm) tissue section from the center of the lymph node prior to pathological analysis. Harvesting alternating 1-2 mm sections of sentinel lymph nodes for H&E, IHC and research studies is something that has been done in numerous clinical studies and as is part of some institutional standard practices. It is accepted that only a small percentage of a lymph node is ever pathologically examined. Much more gets wasted down the cryotome or not seen histologically because of sampling issues or stored in blocks then would be submitted in this study for research purposes. The research tissue would not be evaluated by the pathologist, therefore creating a small risk (1-2%) of understaging patients. A micrometastatic foci, while unlikely, could be missed in these cases if the metastasis is less than 1mm in size. However, the SLN tissue being reviewed is removed from the patient, therefore there is not an increased risk of leaving disease behind as the micrometastatic foci would still be removed as part of the surgical procedure. We do not see this risk as any different than if the patients were not on study and these shaves were not placed on a slide for pathologic review.

Data Safety Monitoring Board

The Mayo Clinic Department of Surgery data safety monitoring board (DSMB) will meet and review the study every six months to assure the safety of the procedure. Specifically, the DSMB will evaluate the progress of the trial, including an interim assessment of participant recruitment and accrual. We will also report to the DSMB the feasibility of the trial, in terms of how many consented patients received the drug from pharmacy, were educated on the self-administration technique, how many doses they administered per their self-assessment log and how many withdrew. The demographics

of the participants are expected to match the demographics of our melanoma population.

Safety assessments

Safety will be evaluated for all treated patients using the NCI CTCAE version 4.0. Safety assessments will be based on medical review of AE reports. Safety will be reviewed by the Department of Surgery DSMB with reference to stopping rules for the study as below.

Stopping rules for patients

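### The study-level safety halt counts removals from the study for toxicity, but no patient-level toxicity rule requires removal from the study, so the counted event is unclear

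*Combined protocol and SAP*

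**What the plan says.** The protocol section on stopping rules for patients describes two different outcomes.

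- **Stopping the drug.** GM-CSF stops for a hazardous allergic reaction, for any grade 3 or higher event, and for "any unacceptable toxicity attributed to GM-CSF at the request of the patient". A list headed "Subjects must be discontinued from any further study therapy for the following reasons" then covers grade 3 or 4 events, events for which the investigator judges further treatment unwise, intercurrent illness and noncompliance. A patient with a "drug related Grade 3 or greater adverse event at the time of discontinuation from study treatment will continue to be followed" until the event resolves or is judged irreversible.
- **Leaving the study.** A second list is headed "Subjects must be discontinued from the study therapy AND withdrawn from the study for the following reasons". Its five reasons are withdrawn consent (whatever the reason), the patient's request, pregnancy, termination of the study, and detention.

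The next section, on stopping rules for the study, gives the halt in one sentence. It begins "The trial will be stopped if 3 consecutive patients or at any time after 6 patients have been treated", continues "if 30% of patients, have been required to be removed from the study due to drug-related toxicities", and ends "accrual will be halted and the study reviewed by the DSMB".

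The section on safety assessments makes this the board's reference: "Safety will be reviewed by the Department of Surgery DSMB with reference to stopping rules for the study as below".

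**The concern.** The halt counts patients who had to be removed from the study because of drug toxicity. The patient-level rules never require that for toxicity; they require only that the drug be stopped. The protocol treats the two outcomes as distinct, marking the second list with a capitalised AND, and nowhere defines *removed* or equates it with stopping GM-CSF.

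Two people applying the rule to the same patients can therefore reach different counts. A literal reader would leave out a patient who stopped GM-CSF for a drug-related grade 3 event and stayed in follow-up. That is the kind of event the halt exists to catch. This is the only numerical safety trigger in the protocol, and the board's scheduled reviews are six months apart. What is at stake is a missed or delayed pre-specified pause, not unseen toxicity: the adverse event reporting section sends all adverse events to the board, and the individual patient stops the drug in any case.

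**Working it through.** The protocol states no operating characteristics for the halt, so there is no figure of its own to reproduce.

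**Step 1: match each toxicity rule to its required outcome.**

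| Toxicity criterion | Required outcome |
|---|---|
| Hazardous allergic reaction | Stop GM-CSF |
| Grade 3 or higher event | Stop GM-CSF |
| Unacceptable toxicity, at the patient's request | Stop GM-CSF |
| Event making further treatment unwise (investigator) | Stop study therapy |

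None leads to the second list. The only entries there through which toxicity could act are withdrawn consent and the patient's own request.

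**Step 2: what the halt needs.** Inputs from the protocol: ten patients in the GM-CSF arm, the three-consecutive limb, and the 30% limb. Assumption: the denominator is GM-CSF-treated patients. The smallest counts reaching 30% are 2 of 6 (33.3%), 3 of 7 (42.9%), 3 of 8 (37.5%), 3 of 9 (33.3%) and 3 of 10 (30.0%).

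**Step 3: formula.** Let q be the probability that a treated patient is counted, independently across patients. Let X be the count among the first six and Y the count among the last four. Three in a row always implies at least three counted, so that limb adds nothing by the tenth patient.

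- Check from the sixth patient: P(halt) = P(X≥2) + P(X=1)·P(Y≥2) + P(X=0)·P(Y≥3)
- Check from the seventh: P(halt) = P(Binomial(10, q) ≥ 3)

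**Step 4: an assumed 30% rate of drug stops for toxicity, check from the sixth.**

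- All stops count, q = 0.30: 0.5798 + 0.3025×0.3483 + 0.1176×0.0837 = 0.695
- Half of those patients also withdraw and only they count, q = 0.15: 0.2235 + 0.3993×0.1095 + 0.3772×0.0120 = 0.272
- A quarter do, q = 0.075: 0.0689 + 0.3047×0.0305 + 0.6264×0.0016 = 0.079
- Patient-initiated withdrawals never count, q = 0: 0

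**Step 5: other assumed rates.**

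| Drug-stop rate | All count, from 6th | Half, from 6th | Quarter, from 6th | All count, from 7th |
|---|---|---|---|---|
| 2% | 0.6% | – | – | 0.1% |
| 3% | 1.3% | – | – | 0.3% |
| 5% | 3.6% | 0.9% | 0.2% | 1.2% |
| 10% | 13.5% | 3.6% | 0.9% | 7.0% |
| 20% | 42.3% | 13.5% | 3.6% | 32.2% |
| 30% | 69.5% | 27.2% | 7.9% | 61.7% |

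**Step 6: which rates are plausible.** The clinical safety section reports a 98-patient adjuvant study in which all grade 3 or 4 events were thought unrelated to the drug. The one-sided 95% upper bound for 0 of 98 is 1 − 0.05^(1/98) = 3.0%. The site also reports no known acute toxicity in the first two weeks beyond minor injection-site irritation, with over 150 patients published. If that informal statement is read as 0 of 150, the bound is 1 − 0.05^(1/150) = 2.0%. Both are upper bounds and concern grade 3 or higher events. Drug stops below grade 3 are also allowed, and the documents give no rate for them.

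**The case against.** The strongest reply is that the sentence most naturally points back to the toxicity rules just above it, so that removal means being taken off the drug. On that reading the halt works, and a safety board is unlikely to prefer a reading that nearly empties its own rule. This is plausible as intent. But the text does not say it, and the preceding section uses the two terms for different outcomes.

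A reader might go the other way and infer that the halt can never fire, with a probability of zero at every toxicity rate. The documents do not support that. Withdrawal from the study is mandatory when consent is withdrawn for whatever reason or when the patient asks to leave, and toxicity can be the reason. Such a patient could be counted. Zero needs the added premise that these withdrawals never count. Nor does the continued follow-up of drug-related grade 3 or higher events prove that the patient remains in the study; it is only consistent with that.

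It is also fair to say that serious drug-related toxicity is expected to be rare, that the 10–30% rows are illustrations without support in the documents, and that individual drug stops and reporting to the board remain as safeguards. These points limit the size of the problem but do not settle what is counted.

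**Conclusion.** The concern holds as a mismatch between the patient-level and study-level rules. No toxicity criterion requires withdrawal from the study, so on a literal reading only patient-initiated withdrawals can feed the halt. Applied that way, the rule undercounts the events it is meant to catch. The loss is large if toxicity is common and small if it is rare, as the protocol expects; the rule is there in case that expectation is wrong. The mismatch itself is plain from the text. The probabilities rest on assumed rates, assumed withdrawal fractions, independence between patients and a denominator of treated patients.

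Two secondary ambiguities sit in the same sentence. It opens by stopping the trial and closes by halting accrual for board review. It also leaves open whether the 30% check starts at the sixth treated patient, where two counted patients suffice, or at the seventh, where three are needed. At a 10% rate with all drug stops counted, that choice alone moves the halt probability from 13.5% to 7.0%.

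**What to change.** The sponsor must reconcile the patient-level and study-level sections so that the halt counts a category the patient-level toxicity rules actually produce, worded identically in both places. As a secondary clarification, the sentence should carry one consequence and state whether the 30% check starts at the sixth or the seventh treated patient. No threshold or clinical rule is proposed here.

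The cost is a one-paragraph wording amendment. The adverse event reporting section already captures the relationship to the product and the action taken for every event, so no new data are needed. Sample size, primary endpoint and procedures are unaffected.
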